7.2 Pulmonary Exacerbation Analysis Sets

106/110 PEx Analysis Set and **108/110 PEx Analysis Set** are defined in **Error! Reference source not found.**. They include the subjects who received TEZ/IVA in parent study or Part A.

Analysis Population Name	Treatment Group	Description
106/110 PE Analysis Set	TEZ/IVA	Subjects randomized to TEZ/IVA in Study 106 and received treatment
	PBO-TEZ/IVA	Subjects randomized to placebo in Study 106 and who received TEZ/IVA in Study 110
108/110 PE Analysis Set	TEZ/IVA	Subjects randomized to IVA-TEZ/IVA sequence or PBO-TEZ/IVA sequence in Study 108 and who received treatment in Period 2 of Study 108
	IVA-TEZ/IVA	Subjects randomized to TEZ/IVA-IVA sequence or PBO-IVA sequence in Study 108 and who received treatment in Period 2 of Study 108 and who received TEZ/IVA in Study 110. Subjects in TEZ/IVA-IVA sequence who did not enroll in Study 110 treatment cohort will also be included in this group if they received treatment in Period 1.
	PBO-TEZ/IVA	Subjects randomized to TEZ/IVA-PBO sequence or IVA-PBO sequence in Study 108 and who received treatment in Period 2 of Study 108 and who received TEZ/IVA in Study 110. Subjects in TEZ/IVA-PBO sequence who did not enroll in Study 110 treatment cohort will also be included in this group if they received treatment in Period 1.

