8.2 Pulmonary Exacerbation Analysis Period

PEx Efficacy Analysis Period is defined as the time period from the first dose of TEZ/IVA in parent study (after the washout period, if applicable) or Study 110 Part A to the date of last efficacy assessment in parent study or Study 110 Part A, as highlighted in grey in [Table 8-1](#). Note for parent Study 108, only Period 2 is pooled.

Similarly, for subjects who participate in another qualified Vertex study before completing Study 110 assessments and re-enroll in Study 110, the PEx Efficacy Analysis Period will exclude the time between the last dose before the discontinuation from Study 110 and the first dose after re-enrollment in Study 110.

Table 8-1 PEx Analysis Period for PEx Analysis Sets			
Analysis Set	Analysis Period		
	Parent Study		Study 110 Part A
106/110 PEx Analysis Set	TEZ/IVA		TEZ/IVA
	PBO		TEZ/IVA
108/110 PEx Analysis Set	Period 1: TEZ/IVA	Period 2: IVA	TEZ/IVA
	Period 1: IVA	Period 2: TEZ/IVA	TEZ/IVA
	Period 1: TEZ/IVA	Period 2: PBO	TEZ/IVA
	Period 1: PBO	Period 2: TEZ/IVA	TEZ/IVA

	Period 1: IVA	Period 2: PBO	TEZ/IVA
	Period 1: PBO	Period 2: IVA	TEZ/IVA

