9.6.2.2 Number of Pulmonary Exacerbations

9.6.2.2.1 Subjects in 106/110 PEx Analysis Set

The number of PEx during the PEx Analysis Period will be analyzed for 106/110 PEx Analysis Set using a negative binomial regression model and reported as event rate along with the 95% CI. The model will include: treatment (TEZ/IVA, PBO-TEZ/IVA), sex, age group at screening (<18, ≥ 18 years old), and parent study baseline ppFEV₁. The logarithm of PEx analysis period duration will be treated as the offset in this model. If the model does not converge, the negative binomial regression model will be replaced with a Poisson regression model.

Similarly the number of PEx (i) requiring hospitalization, and (ii) requiring IV antibiotic therapy will be analyzed.

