9.6.2.3 Time to First Pulmonary Exacerbation

9.6.2.3.1 Subjects in 106/110 PEx Analysis Set

Time-to-first PEx on TEZ/IVA during PEx Analysis Period will be analyzed and plotted by treatment group using the Kaplan-Meier approach.

Subjects without a PEx by the end of PEx Analysis Period will be censored at the time-point corresponding to the end of PEx Analysis Period.

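### SAP 7.2 adds TEZ/IVA-first Study 108 subjects who did not roll over to the 108/110 PEx set, but under the Period 2 note in SAP 8.2 they have no TEZ/IVA time to analyse

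*SAP*

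**What the plan says.** **Who is in the set.** SAP 7.2 opens with a general principle for the PEx sets: "They include the subjects who received TEZ/IVA in parent study or Part A". For the 108/110 set it groups subjects by Period 2 treatment. In the IVA-TEZ/IVA and PBO-TEZ/IVA groups it first requires Period 2 treatment and TEZ/IVA in Study 110, then makes an exception for the sequences that began with TEZ/IVA:

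- IVA-TEZ/IVA group: "Subjects in TEZ/IVA-IVA sequence who did not enroll in Study 110 treatment cohort will also be included in this group"
- PBO-TEZ/IVA group: "Subjects in TEZ/IVA-PBO sequence who did not enroll in Study 110 treatment cohort will also be included in this group"

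Both exceptions carry the same single condition, "if they received treatment in Period 1".

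**What time counts.** SAP 8.2 starts the PEx period at the first TEZ/IVA dose in the parent study (after washout, where there is one) or in Part A, and runs it "to the date of last efficacy assessment in parent study or Study 110 Part A". It refers to grey cells in Table 8-1 and adds: "Note for parent Study 108, only Period 2 is pooled".

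**How the time is used.** In the count model of SAP 9.6.2.2.1, "The logarithm of PEx analysis period duration will be treated as the offset in this model"; 9.6.2.2.2 carries this over to the 108/110 set. For time to first PEx, SAP 9.6.2.3.1 has event-free subjects "censored at the time-point corresponding to the end of PEx Analysis Period", and 9.6.2.3.2 carries that over too.

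**The concern.** Membership and person-time are set by two rules that do not meet. Section 7.2 admits certain subjects because of their Period 1 treatment; the note in 8.2 removes Period 1 from the analysis. These subjects had no TEZ/IVA in Period 2 and none in Study 110.

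A programmer cannot follow both rules. Either subjects whom 7.2 includes are dropped, or time that the note excludes is counted. If that choice is made at programming, whose time and events enter the rates is settled after the data exist. Counting Period 1 for non-rollovers only would also make a subject's person-time depend on the later failure to enrol.

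The outputs at stake are the 108/110 PEx rates (all, hospitalised, IV-treated) and the time-to-first-PEx curves.

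**Working it through.** **Step 1. Apply both rules to every sequence.** The sequences come from Table 8-1, membership from SAP 7.2, and countable time from the 8.2 note (Period 2 plus Study 110).

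| Study 108 sequence | Group | Entered Study 110: TEZ/IVA time | Did not enter: in set? TEZ/IVA time |
|---|---|---|---|
| IVA, then TEZ/IVA | TEZ/IVA | Period 2 + Study 110 | In; Period 2 |
| PBO, then TEZ/IVA | TEZ/IVA | Period 2 + Study 110 | In; Period 2 |
| TEZ/IVA, then IVA | IVA-TEZ/IVA | Study 110 | **In; none** |
| PBO, then IVA | IVA-TEZ/IVA | Study 110 | Not in set |
| TEZ/IVA, then PBO | PBO-TEZ/IVA | Study 110 | **In; none** |
| IVA, then PBO | PBO-TEZ/IVA | Study 110 | Not in set |

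Of the 12 sequence-by-rollover cells, 10 are in the set and 8 of those have TEZ/IVA time. The two without are exactly the two that 7.2 adds by name. Their duration is 0, log(0) is undefined, and there is no period end at which to censor.

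**Step 2. Which rule does other text support?**

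- For the note: Protocol 12.3.1 places the first active dose for Study 108 in Treatment Period 2, for the Efficacy Analysis Period as well as the TE Period, and takes the Study 108 baseline from Period 2. The washout qualifier in the opening of SAP 8.2 also fits Period 2.
- Against the note: the opening principle of SAP 7.2, and Protocol 12.3.4.2, which starts time to first PEx at the first dose of combination therapy.
- Unknown: the shading of Table 8-1, which is not visible in the text available to me. It can show which rule was meant but cannot make both hold.

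**Step 3. Size.** SAP 6.2 gives 227 rollovers from Study 108. Protocol 12.1 gives up to 300 potentially eligible. Non-rollovers are not counted anywhere. Assumptions: at most 300 randomised; rollovers and non-rollovers each spread equally over six sequences; period length P = 6-12 weeks; mean Study 110 follow-up F = 48-96 weeks.

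- Rollovers per group (two sequences): 227 × 2/6 = 75.7
- Added non-rollovers per group (one sequence): 0 to (300 − 227)/6 = 12.2
- Share of group N, upper end: 12.2/(12.2 + 75.7) = 13.9%
- Share of person-time if their Period 1 alone counts, 12.2·P/(12.2·P + 75.7·F):
  - P = 6, F = 96: 73/(73 + 7,264) = 1.0%
  - P = 12, F = 48: 146/(146 + 3,632) = 3.9%
  - with none added: 0%
- Change in the crude group rate = s(k − 1), with s the person-time share and k the rate in the added time relative to the rest. At s = 3.9%: k = 0.5 gives −1.9% and k = 2 gives +3.9%.

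**Step 4. If Period 1 counted for all TEZ/IVA-first subjects.** About 227/6 = 38 rollovers per group would also gain Period 1 time and events. Period 1 would then make up between 38 × 6/(38 × 6 + 75.7 × 96) = 3.0% (no non-rollovers) and (38 + 12) × 12/((38 + 12) × 12 + 75.7 × 48) = 14.2% of group person-time. That is a larger change than the non-rollovers alone would make.

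**The case against.** The best defence is that 8.2 defines the period by the shaded cells. If the Period 1 TEZ/IVA cells are grey, the intention is clear and 7.2 is consistent with it. That would identify the faulty sentence, but the written note would still be wrong and need correcting.

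A second defence is that, under the note, these subjects simply contribute nothing, so the fault is two redundant sentences in a descriptive analysis. That is a fair account of the consequence under that reading and is why the point is minor. It does not tell a programmer which reading to take.

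It can also be argued that the protocol decides in favour of Period 2. Protocol 12.3.1 is good support and is the reason for preferring one fix over the other. It is not conclusive: Protocol 12.3.4.2 points the other way. The protocol's limit of the FAS to subjects dosed in Study 110 does not settle it either, because SAP 7.2 sets up separate PEx sets whose TEZ/IVA groups do not require Study 110 dosing.

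Three stronger readings are tempting but not supported:

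- That 8.2 counts everything from the Period 1 dose to the last parent-study visit, so that washout and ivacaftor or placebo time passes as TEZ/IVA time. The end of that sentence alone could suggest it, but the washout qualifier at its start and the note that follows tell against it.
- That 12 per group is an upper bound. The figure of 300 is a planning number for eligible subjects, and non-enrolment need not be equal across sequences.
- That the 108/110 TEZ/IVA group is wholly untouched. SAP 9.6.2.2.2 fits one model with shared covariate terms, and a negative binomial model ordinarily has one dispersion parameter, so that group's model-based rate and interval could shift slightly.

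**Conclusion.** The conflict is certain on the wording: two cells of the 108/110 PEx set have zero TEZ/IVA time under the 8.2 note, and the planned offset and censoring cannot be computed for them. Which sentence is wrong is not certain. The balance of the visible text favours the note.

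The effect is minor. On the assumptions in the working, about 0-12 non-rollovers per group are involved, with 0-3.9% of group person-time if their Period 1 alone counts and none under the note. The true number cannot be derived from the documents.

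The direct effect is on the IVA-TEZ/IVA and PBO-TEZ/IVA groups, with a possible slight effect on the TEZ/IVA group's model-based rate. That group's crude and Kaplan-Meier results, the 106/110 set, the MMRM analyses and the primary safety analysis are unaffected. SAP 9.6.2 plans no between-group tests.

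**What to change.** State in words which cells of Table 8-1 count, so that the rule does not rest on shading.

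**Default.** Keep the 8.2 note, delete the two sentences in 7.2 that add non-rollovers, and state in 9.6.1.5 that time zero is the first TEZ/IVA dose within the pooled period (Period 2 or Study 110). The last item matters because, for TEZ/IVA-first subjects who did roll over, the first TEZ/IVA dose could otherwise be read as the Period 1 dose. The cost is wording only; the deleted subjects contribute no time under the note anyway.

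**Only if the shading marks the Period 1 TEZ/IVA cells.** Correct the 8.2 note instead. Count Period 1 TEZ/IVA time and events for every TEZ/IVA-first subject, rolled over or not. Exclude washout and Period 2 ivacaftor or placebo time from both events and offset. Record the change as a departure from Protocol 12.3.1. The cost is programming the off-TEZ/IVA gap into the count and time-to-event datasets, and changed data for about 38 rollovers per group (227/6, assuming equal sequences).

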7.3 Safety Analysis Set

The **Safety Set** is defined as all subjects who have received at least 1 dose of study drug in Part A irrespective of their genotype. The Safety Set is to be used for the safety analyses unless otherwise specified.

7.4 Parent Study Safety Analysis Set

The safety results from Study 106 will be presented along with Part A results. The definition of **106 Safety Set** is the same as defined in the SAP/CSR for Study 106, i.e., subjects who received at least 1 dose of study drug in Study 106.

The treatment group assignment is the same as in Study 106, as illustrated in [Table 7-3](#).

Table 7-3 Treatment Group for 106 Safety Set	
Treatment Group	Description
TEZ/IVA	Subjects who received at least 1 dose of TEZ/IVA in the parent study (including subjects randomized to TEZ/IVA or who received TEZ/IVA by error)
PBO	Subjects who take only placebo during the entire parent study period

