6.2 Sample Size and Power

Part A

Treatment Cohort

1,044 eligible subjects are enrolled from the following parent studies:

- 23 subjects from Study 103.
- 464 subjects from Study 106.
- 159 subjects from Study 107.

- 227 subjects from Study 108.
- 138 subjects from Study 109.
- 33 subjects from Study 111.

Observational Cohort

No patient enrolled in observational cohort.

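### Study 106 safety results are set alongside a pooled Study 110 Safety Set in which 44.4% of enrolled subjects came from Study 106, so differences mix case mix with treatment duration

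*SAP*

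**What the plan says.** SAP 7.4 (Parent Study Safety Analysis Set) states: "The safety results from Study 106 will be presented along with Part A results". The 106 Safety Set is defined as "subjects who received at least 1 dose of study drug in Study 106" and is split into TEZ/IVA and PBO groups. Protocol 8.2.1 describes Study 106 as the homozygous study.

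The Part A side is the Safety Set of SAP 7.3: "all subjects who have received at least 1 dose of study drug in Part A irrespective of their genotype". SAP 9.7 bases the adverse event, laboratory, ECG, vital sign and oximetry summaries on this set over the 110 TE Period. The TEAE tables give counts and exposure-adjusted event rates. SAP 9.7.1.2 refers to a column for the Study 110 Safety Set, which fits a side-by-side layout, although the table shells are not shown.

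SAP 6.2 gives the composition: "1,044 eligible subjects are enrolled from the following parent studies", of which "464 subjects from Study 106", "159 subjects from Study 107" and "227 subjects from Study 108", with 138 from Study 109, 23 from Study 103 and 33 from Study 111.

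SAP 9.7.1 also places a TEAE table for each of the six parent studies in the Study 110 report, each covering its own parent period. No Study 110 TEAE summary by parent study or genotype is specified. SAP 9.7.3 mentions treatment group for the ECG threshold counts, but the SAP does not define such groups for the Safety Set.

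**The concern.** Long-term safety is the primary objective. A reader who sees Study 106 results next to Study 110 results will ask whether event rates rise, fall or hold steady beyond the parent study. The two displays describe different populations. One is entirely F/F from a single study. The other combines F/F subjects from three studies with heterozygous subjects from three more, and it does not separate subjects continuing TEZ/IVA from those starting it after placebo or ivacaftor. A rate change that reflects only who is in the column could be taken for an effect of longer treatment, and a real change could be hidden.

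The SAP itself makes this reading likely. Protocol 12.3.2 says Study 110 data will not be analysed in isolation, because durations of parent treatment differed, and will be integrated with parent data for each subject. SAP 8.3 and 9.7.1 instead confine the adverse event analysis to the 110 TE Period. Setting parent results against Study 110 results is then the way left to judge change over time.

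**Working it through.** **1. Reproduce the total (SAP 6.2).** 23 + 464 + 159 + 227 + 138 + 33 = 1,044, which agrees with the SAP.

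**2. Composition by headcount.** Genotypes are from Protocol 8.2.1 (106 homozygous; 107, 108 and 109 heterozygous) and SAP 9.6.2 (103 and 111 F/F).

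| Source | n | Share of 1,044 |
|---|---|---|
| Study 106 (F/F) | 464 | 44.4% |
| Studies 103 + 111 (F/F) | 23 + 33 = 56 | 5.4% |
| Studies 107 + 108 + 109 (heterozygous) | 159 + 227 + 138 = 524 | 50.2% |
| All except Study 106 | 580 | 55.6% |

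These are shares of enrolled subjects. The Safety Set requires at least one dose, and its size is not stated separately.

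**3. Weight in an exposure-adjusted rate.** Here the weight is person-time, which the documents do not give. SAP 7.1 says subjects from Studies 107 and 109 were discontinued early from Study 110; they number 159 + 138 = 297. Assume equal exposure for everyone else, and let the 297 have a fraction f of that exposure. The remaining non-106 subjects number 580 − 297 = 283, and all subjects outside 107 and 109 number 1,044 − 297 = 747. Then

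non-106 share of person-time = (283 + 297f) / (747 + 297f).

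| f | Calculation | Non-106 share | Study 106 share |
|---|---|---|---|
| 1 | 580 / 1,044 | 55.6% | 44.4% |
| 0.5 | 431.5 / 895.5 | 48.2% | 51.8% |
| 0 (limit) | 283 / 747 | 37.9% | 62.1% |

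**4. Effect on the pooled rate.** Suppose Study 106 rollovers keep exactly their Study 106 event rate, and the other subjects' rate is r times that rate. With w the Study 106 share of person-time,

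pooled rate / Study 106 rate = w + (1 − w)r,

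so the shift is (1 − w)(r − 1). For an illustrative r of 0.8 or 1.2:

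- f = 1: 0.556 × 0.20 = 11.1%
- f = 0.5: 0.482 × 0.20 = 9.6%
- f = 0: 0.379 × 0.20 = 7.6%

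The pooled rate moves by these amounts, down or up, with no change over time in any subject. The 20% is an assumption; the documents give no event rates.

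**5. Does anything already planned remove this?** Exposure adjustment corrects for length of follow-up, not for genotype, source study or prior arm. The six parent-study TEAE tables cover the parent periods and leave the Study 110 results undivided.

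**The case against.** The strongest reply is that no planned comparison is being confounded. Protocol 12.3.2 prespecifies pooling of safety over all subjects, Protocol 12.3.5 calls the safety analysis descriptive, and SAP 7.4 plans no difference, ratio or test between Study 106 and Study 110. This stands. A reader might infer that an invalid comparison is planned; the documents do not support that, and the point is one of interpretation.

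A reader might also infer that Study 106 is the only placebo context in the safety report. That does not follow. SAP 9.7.1 includes a TEAE table for every parent study, and SAP 7.2 and 8.2 show that Study 108, a heterozygous study, had placebo periods. Whether those tables are split by arm is not stated. They let a reader look for differences between source studies during the parent periods, but not within Study 110.

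Two further limits on size are fair. The headcount share overstates the non-106 weight in exposure-adjusted rates if the 107 and 109 subjects contributed less time, so 11.1% is the top of the range. Also, 56 of the 580 non-106 subjects are F/F, so the subjects from parent studies of a different genotype number 524, not 580.

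Finally, restricting Study 110 to Study 106 rollovers is not fully like-for-like. The 106 Safety Set includes everyone dosed, whereas SAP 6.1 and Protocol 9.1 bar from the Treatment Cohort anyone who permanently discontinued parent treatment. Later rates could be lower through that selection alone. This stands, and the remedy has to address it.

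**Conclusion.** The concern holds as a limit on what the display can show. By headcount, 55.6% of those enrolled came from outside Study 106 and 50.2% from heterozygous studies. Under the exposure assumption above, non-106 subjects supply 37.9% to 55.6% of person-time, and a 20% difference in their event rate would shift the pooled rate by about 7.6% to 11.1% without any effect of duration. These figures rest on enrolled counts standing in for the Safety Set, on equal exposure outside Studies 107 and 109, and on an assumed rate difference. The mixing itself follows from the SAP's own definitions and needs none of these assumptions. It invalidates no test. It is a low-cost improvement to the reporting of the primary objective.

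**What to change.** Keep the pooled Study 110 column. Add to the TEAE tables two Study 110 columns for subjects from Study 106, split by parent arm (TEZ/IVA and PBO-TEZ/IVA). SAP 7.1 already defines these groups for efficacy.

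State in SAP 7.4 and in the table footnotes that the pooled column should not be read against the 106 Safety Set.

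Then do one of the following about selection:

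- show the Study 106 results also for the subjects who rolled over; or
- footnote that the 106 Safety Set includes subjects who did not complete parent treatment, whom Study 110 excludes, so selection of completers remains.

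If the first option is taken, note that TEAEs leading to permanent discontinuation in Study 106 will be essentially absent among rollovers by design, so that row says nothing about change over time.

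No new data, tests or analysis sets beyond existing groupings are needed. The cost is wider tables and some programming.

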8 ANALYSIS PERIODS

8.1 Efficacy Analysis Period

110 Efficacy Analysis Period is defined as the time period from the 1st dose of study drug in Part A to the date of last efficacy assessment in Part A.

For subjects who participate in another qualified Vertex study before completing Study 110 assessments and re-enroll in Study 110, 110 Efficacy Analysis Period will exclude the time between the last dose before the discontinuation from Study 110 and the first dose after re-enrollment in Study 110.

